- Determine if age, use of angiotensin converting enzyme inhibitors, the duration of pre-hospitalization symptoms, or the presence or absence of hypertension, cardiovascular disease, asthma, diabetes mellitus, or COPD are predictive of clinical outcome defined by the primary endpoint or any secondary endpoint.
- Determine if baseline, Day 8 or Day 15 values for D-dimer, IL-6, LDH, ferritin, total WBC, absolute neutrophil count (ANC), absolute lymphocyte count (ALC), or testosterone are predictive of clinical outcome defined by the primary endpoint or any secondary endpoint.
- Determine if degarelix + BSC as compared to placebo + BSC reduces nasopharyngeal (NP) epithelial or peripheral blood mononuclear cell (PBMC) TMPRSS2 expression, NP and plasma viral load, or serum cytokine (TNF α , IL-1 β , IL-6) levels.
- Determine whether germline genomic factors are predictive of clinical outcome defined by the primary endpoint or any secondary endpoint. This analysis is optional and is contingent on obtaining adequate number of samples.
- To determine the temporal onset of anti-viral antibodies.

Definition of Need for Ongoing Hospitalization (i.e. discharged): Patients who no longer require hospitalization on an acute bed ward for COVID-19 or its complications will be considered discharged (i.e. do not need ongoing hospitalization). For example, if a patient does not require ongoing hospitalization on an acute care ward due to COVID-19 but has remained on a non-acute inpatient unit (e.g. physical rehabilitation unit), the patient will be considered discharged for the purpose of the endpoints of this study. However, if the patient has a major complication of the hospitalization for COVID-19 (e.g. stroke) and requires ongoing hospitalization for this complication in an acute care bed, then this the patient will be considered as hospitalized for the purpose of endpoint definition even if the COVID-19 itself is deemed to have been adequately treated (i.e. no ongoing signs and symptoms that are directly due to COVID-19).

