The primary study endpoint will be the composite outcome of mortality, ongoing need for hospitalization, and ECMO or mechanical intubation at 15 days after randomization. This outcome will be compared according to assigned treatment groups, using Pearson χ^2 test. The test for differences between the treatment groups in the primary outcome will be conducted at an overall α -level of 0.05 (i.e. $\alpha = 0.006$ for mid-term interim analysis, $\alpha = 0.044$ for the final analysis). If a patient drops out from the study, then he will be considered as a failure. Additional analyses will be conducted using logistic models to adjust for other clinical factors, such as age, hypertension, and COPD. Logistic regression will be used for the primary endpoint ($y = 1$ if a composite outcome, otherwise $y = 0$) analysis with the treatment group as the testing factor (x). The following covariates will be included in the model: age (z_1), hypertension (z_2), and COPD (z_3), site (z_4). Given the composite outcome probability $p = p(y = 1|x, z_1, z_2, z_3)$, the basic model is defined as follows:

$$\text{Logit}(p) = \ln\left(\frac{p}{1-p}\right) = \beta_0 + \beta_1 x + \beta_2 z_1 + \beta_3 z_2 + \beta_4 z_3$$

Odds ratio and 95% confidence interval (CI) will be presented using SAS PROC GENMOD or PROC LOGSTIC. If the coefficient for treatment effect is significant, then

the null hypothesis will be rejected. Logistic models will be tested for goodness of fit. We will assess goodness-of-fit using the statistic -2 log likelihood, which has a χ^2 distribution under the null hypothesis that all the explanatory variables in the model are zero. We will also consider the Akaike Information Criterion statistic and the Schwartz Criterion statistic, both of which adjust the -2-log likelihood for the number of items in the model. Models that show lack of fit will be reconsidered for the inclusion of additional variables or use of alternate models with assumptions that are better met by the study data. One alternate model if model fit is poor for logistic regression is a log-linear model.

Further, Cochran Mantel-Haenszel method will be used to adjust for three randomization stratification factors (Age: <65 vs. \geq 65, History of hypertension: yes vs. no, and Influenza severity scale: 3 vs 4/5) using SAS PROC FREQ as one of the sensitivity analyses for the primary efficacy endpoint.

Secondary Endpoint Analyses

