Secondary endpoints included in the data analysis are the composit endpoint at 30 days after randomization, time to clinical improvement, inpatient mortality, length of hospital stay, length of intubation for mechanical ventilation, time to normal temperature, and the maximum severity of COVID-19 illness, which are defined in the endpoint section. The secondary endpoint analyses will be adjusted for multiplicity with a α -level of 0.0071 for each endpoint.

The composite outcome of mortality, ongoing need for hospitalization, and ECMO or mechanical intubation at 30 days after randomization as a secondary endpoint will be analyzed using the methods described in the the primary endpoint analysis.

For the time to clinical improvement as defined by a decline of 2 categories or more from the baseline on the modified 7-category ordinal scale of clinical status of hospitalized influenza patients (influenza scale, see Appendix A) or hospital discharge (see section 2 for definition of discharge) whichever comes first, survival analysis techniques will be used to analyze the time-to-event data for this endpoint. Patients whose conditions getting worse or died or withdraw from the study without clinical improvement will be censored. Kaplan-Meier analysis will be used to compare the two curves of the time to the clinical improvement over the patient follow-up time between the two treatment groups and a log-rank statistic will be used to test the equality of the survival function estimates of the two treatment groups using SAS PROC LIFETEST. Kaplan-Meier curves will be created. Additional analysis will be conducted using the Cox's Proportional Hazards model to test the treatment efficacy of the treatment intervention on the time until endpoint events adjusted for three prognostic factors: age, hypertension, and COPD. The hazard ratio and 95% confidence interval (CI) will be presented using SAS PROC PHREG. If the coefficient for treatment effect is significant, then the null hypothesis will be rejected. The regression model will be checked for the model assumption, adequacy, and the goodness of fit. If the model shows lack of fit, then alternate models with assumptions that are better met by the study data will be considered.

For mortality endpoint data analysis, the treatment effect will be analyzed initially with a Pearson χ^2 test and logistic regression will also be performed using SAS PROC

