LOGISTIC by taking account of prognostic factors described in the primary endpoint analysis.

For the length of hospital stay data analysis, medians (interquartile ranges) will be presented and Wilcoxon tests, a nonparametric method, will be performed to compare the medians of the length of hospital stay between the two treatment groups using SAS PROC NPAR1WAY. In addition, a quantile regression will be used to test the effect of the treatment on the time until the clinical event adjusted for prognostic factors described in the primary endpoint analysis.

For the length of intubation for mechanical ventilation data analysis, nonparametric analyses will be performed as described in the length of hospital stay analysis.

For time to normal temperature data analysis, survival analysis techniques will be used as described in the time to the clinical endpoint analysis using SAS PROC LIFETEST and PROC PHREG.

For the maximum severity of COVID-19 illness data analysis, Pearson χ^2 test will be performed for this categorical endpoint using SAS PROC FREQ initially. Given the endpoint is also an ordinal variable, Cochran–Armitage test will be performed to test the ordinal trend tendency using SAS PROC FREQ. in addition to the frequency analysis, proportional odds logistic regression will also be performed using SAS PROC LOGISTIC by taking account of the factors of age, hypertension, COPD, and the baseline influenza scale (see Appendix A).

Exploratory Endpoint Analyses

Clinical and Laboratory Prognostic Factors

Exploratory analyses will be performed to identify the impact of clinical and laboratory prognostic factors on the primary endpoint or any secondary endpoint. Clinical factors include age, presence or absence of COPD, hypertension, or cardiovascular disease, or use of angiotensin converting enzyme inhibitors. Laboratory measurements including D-dimer, IL-6, LDH, ferritin, total WBC, absolute neutrophil count (ANC), absolute lymphocyte count (ALC), and testosterone are measured during the patient's hospital stay. Further germline genomic factors will also be analyzed if feasible as prognostic factors for the study outcomes for part of the patients.

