For continuous variables, the sample size, mean, SD, median, minimum, and maximum values for each intervention will be presented for each parameter at each data collection time point and tested using SAS PROC TTEST between the treatment groups. If a variable is not normally distributed the non-parametric method will be applied using SAS PROC NPAR1WAY. For categorical variables, the number and percentage of patients by the treatment group will be tabulated and tested based on Pearson χ^2 test using SAS PROC FREQ.

Univariate correlation with the primary endpoint or any categorical secondary endpoint will be assessed for each clinical and laboratory factor based on logistic regressions using SAS PROC LOGISTIC. For the secondary endpoints of time to events data, univariate analysis will be performed based on Cox regressions using SAS PROC PHREG. For the secondary endpoints of length of hospital stay and length of intubation for mechanical ventilation, nonparametric univariate analysis will be performed based on Spearman correlation method using SAS PROC CORR for the continuous prognostic factors, whereas Mann–Whitney U or Wilcoxon rank-sum test will be performed for the categorical prognostic factors using SAS PROC NPAR1WAY. For those prognostic factors significantly associated with the primary and secondary outcomes from the univariate analyses, multiple regressions will be performed by adjusting some other prognostic factors identified from the univariate analyses. The multiple regressions will be performed as described in the primary analysis and each corresponding secondary endpoint analysis.

Viral Load, Cytokines Levels, and TMPRSS2 Expression

To explore the mechanisms that underlie treatment effect, nasopharyngeal (NP) epithelial or peripheral blood mononuclear cell (PBMC) TMPRSS2 expression, NP and plasma viral load, or serum cytokine (TNF- α , IL-1 β , IL-6) levels will be tested among the patients from the Great Los Angeles site, only.

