### **3.7.3 Exploratory Endpoint Analyses**

#### Clinical and Laboratory Prognostic Factors

Exploratory analyses will be performed to identify the impact of clinical and laboratory prognostic factors on the primary endpoint or any secondary endpoint. Clinical factors include age, presence or absence of COPD, hypertension, or cardiovascular disease, or use of angiotensin converting enzyme inhibitors. Laboratory measurements including D-dimer, IL-6, LDH, ferritin, total WBC, absolute neutrophil count (ANC), absolute lymphocyte count (ALC), hemoglobin, hematocrit, platelet counts, and testosterone are measured during the patient's hospital stay. Further germline genomic factors will also be analyzed if feasible as prognostic factors for the study outcomes for part of the patients.

For continuous variables, the sample size, mean, SD, median, minimum, and maximum values for each treatment will be presented for each parameter at each data collection time point and tested using SAS PROC TTEST between the treatment groups. If a variable is not normally distributed the non-parametric method will be applied using SAS PROC NPAR1WAY (Table 3.7.3.1). For categorical variables, the number and percentage of participants by the treatment group will be tabulated and tested based on Pearson  $\chi^2$  test using SAS PROC FREQ (Table 3.7.3.2).

Univariate correlation with the primary endpoint or any categorical secondary endpoint will be assessed for each clinical and laboratory factor based on logistic regressions using SAS PROC LOGISTIC (Table 3.7.3.3). For the secondary endpoints of time to events data, univariate analysis will be performed based on Cox regressions using SAS PROC PHREG (Table 3.7.3.4). For the secondary endpoints of length of hospital stay and length of intubation for mechanical ventilation, nonparametric univariate analysis will be performed based on Spearman correlation method using SAS PROC CORR for the continuous prognostic factors, whereas Mann–Whitney U or Wilcoxon rank-sum test will be performed for the categorical prognostic factors using SAS PROC NPAR1WAY (Table 3.7.3.5). For those prognostic factors significantly associated with the primary and secondary outcomes from the univariate analyses, multiple regressions will be performed by adjusting some other prognostic factors identified from the univariate analyses. The multiple regressions will be performed as

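### The one-factor significance screen for prognostic factors can miss ACE-inhibitor use if its effect opposes that of hypertension, and three of the eight named clinical factors are missing from the analysis list

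*Protocol*

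**What the plan says.** Protocol section 10 (Clinical and Laboratory Prognostic Factors) and SAP 3.7.3 set out two steps. The first is a one-factor test: "Univariate correlation with the primary endpoint or any categorical secondary endpoint will be assessed for each clinical and laboratory factor based on logistic regressions", with Cox models, Spearman correlations or rank tests for the other endpoints. The second step depends on the first: "For those prognostic factors significantly associated with the primary and secondary outcomes from the univariate analyses, multiple regressions will be performed", and these are adjusted "by adjusting some other prognostic factors identified from the univariate analyses". A further sentence sets the form: "The multiple regressions will be performed as described in the primary analysis and each corresponding secondary endpoint analysis".

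The models it points back to are fixed. The primary logistic model carries age, hypertension and COPD (the protocol text also names site), and the Cox model is "adjusted for three prognostic factors: age, hypertension, and COPD". ACE-inhibitor use is in neither.

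The two lists of clinical factors differ. The exploratory objective in Protocol section 2 names age, ACE-inhibitor use and "the duration of pre-hospitalization symptoms, or the presence or absence of hypertension, cardiovascular disease, asthma, diabetes mellitus, or COPD are predictive of clinical outcome", which makes eight; SAP 2.4.3 agrees. The analysis text says: "Clinical factors include age, presence or absence of COPD, hypertension, or cardiovascular disease, or use of angiotensin converting enzyme inhibitors", which makes five. Asthma, diabetes and duration of symptoms before admission are absent, although SAP 3.5.2 and 3.5.3 summarise all three at baseline.

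**The concern.** A one-factor p-value is a poor entry rule when candidate factors are associated. A factor whose effect appears only after adjustment fails the screen, and the model that would reveal it is never fitted. A factor with no effect of its own can pass as a proxy for another.

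ACE-inhibitor use is the exposed case. The protocol asks about it by name, alongside conditions for which such drugs are commonly prescribed, and no other analysis would give an adjusted estimate for it. For a factor that fails the screen, the confounded one-factor result is all that is reported. At stake is the answer to one exploratory question. The list mismatch is separate and simpler: three stated questions have no listed analysis.

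**Working it through.** **Inputs from the documents.** Event rates 60% (placebo) and 35% (degarelix), 2:1 allocation, 198 randomised (132 + 66), 186 evaluable (124 + 62): Protocol section 10. Two-sided 0.05 for tests without their own level: SAP 3.1.2.

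**The plan's own figure.** Two-proportion formula, pooled variance, no continuity correction, 90% power: 61 + 122 = 183, within 3 of the stated 186. Power at 62 + 124 is 90.5%. The sample size and event rate are therefore a sound base. The documents give no figure for the screen itself.

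**Events.** Overall rate (2 × 35% + 60%) / 3 = 43.3%. Events: 198 × 0.433 ≈ 86. Eight factors plus arm make nine terms: 86 / 9 ≈ 9.5 events per term.

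**Assumptions not in the documents.** 60% of men hypertensive; ACE-inhibitor use in 30%, 50% or 70% of hypertensive men and 5% of others; conditional odds ratios as stated below.

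**Why masking occurs (50% use; OR 2.0 for hypertension, 0.5 for the ACE inhibitor).** A baseline odds of 0.626 gives the overall rate of 43.3%:

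| Group | Share | Odds | Risk |
|---|---|---|---|
| Hypertension, ACE inhibitor | 30% | 0.626 × 2 × 0.5 = 0.626 | 0.385 |
| Hypertension, none | 30% | 0.626 × 2 = 1.252 | 0.556 |
| No hypertension, ACE inhibitor | 2% | 0.626 × 0.5 = 0.313 | 0.238 |
| Neither | 38% | 0.626 | 0.385 |

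- Risk with the ACE inhibitor: (0.30 × 0.385 + 0.02 × 0.238) / 0.32 = 0.376. Without: (0.30 × 0.556 + 0.38 × 0.385) / 0.68 = 0.460. One-factor OR = (0.376 / 0.624) / (0.460 / 0.540) ≈ 0.71, against a true 0.5.
- Risk with hypertension: (0.385 + 0.556) / 2 = 0.4705. Without: (0.02 × 0.238 + 0.38 × 0.385) / 0.40 = 0.378. One-factor OR ≈ 1.46, against a true 2.0.

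Over 30–70% use, the one-factor ORs are 0.65–0.78 and 1.27–1.68. Neither factor passes the screen in 45–72% of simulated trials (198 men, Wald p < 0.05, 1,500 runs per scenario).

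**Screen against joint model, for ACE-inhibitor use.** The screened column is the proportion of trials in which it passes and then stays significant with hypertension forced into the second step, the reading most favourable to the plan.

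| True effects | With screen | Joint model |
|---|---|---|
| Opposing (hypertension 2.0, ACE inhibitor 0.5) | 11–19% | 38–49% |
| Agreeing (both 2.0) | 42–48% | 42–48% |
| ACE inhibitor only | 36–41% | 40–47% |

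**No ACE-inhibitor effect (hypertension OR 2.0).** The one-factor test is falsely significant in 10–33% of trials, against 5% in a joint model. After the planned second step with hypertension in the model, the rate is about 2–3%.

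**Agreeing effects.** The one-factor OR for the ACE inhibitor is 2.55–3.04 where the true value is 2.0: it passes, but the one-factor estimate is inflated.

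**Few-event endpoints.** Applying the 17% mortality and 11% ventilation/ECMO that the plan cites from an earlier trial: 198 × 0.17 ≈ 34 deaths, or about 3.7 per term with nine terms; 198 × 0.11 ≈ 22 ventilated men.

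**The case against.** The case for leaving the text alone has real force.

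- **Masking is conditional.** Positively associated factors hide each other only when their effects oppose, and the documents give no direction for either. The table shows no loss if the effects agree and little if only the ACE inhibitor acts. This stands, and it limits the claim.
- **Hypertension is not lost.** A reader might infer that both factors are dropped before adjustment. The documents do not support that: hypertension is a fixed covariate in the primary logistic and Cox models and a stratification factor, and SAP 3.7.1 reports a Wald test for each covariate. What remains concerns ACE-inhibitor use.
- **The second step removes most false positives.** A reader might take the 10–33% as the plan's error rate. It is the rate of the first step only. What remains is that the one-factor results are themselves planned output.
- **Referring back to the primary model might rescue the rule.** It does not, because the screen comes first: the 11–19% already grants that hypertension is forced in.
- **The prescribing link is outside knowledge.** SAP 3.5.3 records ACE-inhibitor use in the 30 days before admission and nothing about why. The association and its strength are my assumptions.
- **The shorter list may be illustrative.** It is introduced as what the factors include, so it would go too far to say that diabetes cannot enter the adjustment. The lists still disagree and need reconciling.
- **A nine-term model does not suit every endpoint.** This stands, and the fix allows for it.

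**Conclusion.** The point holds in a limited form. Entry to the adjusted prognostic model, and the choice of adjusters, both rest on one-factor significance, and ACE-inhibitor use has no other route to adjustment. It can be missed if its effect opposes that of hypertension: about 11–19% found with the screen against 38–49% without, at odds ratios of 0.5 and 2.0. Its one-factor result can be confounded by hypertension in either direction if the two are associated. The size rests on assumed prevalences, association and odds ratios. The screen itself and the five-against-eight mismatch are in the text and need no assumption.

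The documents do not support concluding that the ACE-inhibitor question will be answered wrongly, or that the efficacy result is in doubt. SAP 3.7 treats these analyses as hypothesis-generating, and the treatment comparison does not depend on them. This is a worthwhile improvement of low severity.

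**What to change.** In Protocol section 10 (Clinical and Laboratory Prognostic Factors) and SAP 3.7.3:

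1. For the primary endpoint, replace the screen with one prespecified logistic model containing the eight baseline clinical factors of Protocol section 2 plus treatment arm. At the least, always adjust ACE-inhibitor use for age, hypertension, cardiovascular disease and diabetes, whatever the one-factor p-values.
2. Present one-factor results as description only.
3. For endpoints with few events, such as inpatient mortality and duration of intubation, use a smaller fixed set: ACE-inhibitor use, hypertension, age and arm. Use Firth penalisation for the logistic models. With about 22 ventilated men, four terms leave 22 / 4 = 5.5 men per term, so the intubation results should be described as very imprecise.
4. Add asthma, diabetes and duration of symptoms before admission to the analysis list, so that it matches Protocol section 2 and SAP 2.4.3.

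The cost is wording in two documents and no new data, since SAP 3.5.1 to 3.5.3 already cover all eight factors. The statistical price is somewhat wider intervals for factors that are not correlated with the others.

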Best supportive care will include all treatments that would be applied irrespective of patient enrollment and includes but is not limited to supplemental oxygen, antibiotics, vasopressor support, peritoneal or hemodialysis, antibiotics, intravenous fluids. The treatment landscape for COVID-19 is rapidly evolving. Accordingly, the clinical trial will allow for updates to the allowed treatments. For example, emergency authorization of remdesivir was recently granted, so remdesivir usage is allowed prior to or during study enrollment. In addition, use of convalescent plasma is not uncommon, is available through an expanded access program and will be allowed prior to or during study enrollment. New treatments will have a drug utilization report assessment prior to use to identify overlapping toxicities prior to use of a new treatment.

Off-label use of other agents or interventions will be allowed. For example, anti-coagulation is recommended by various societies, including the American Society of

Hematology. Off-label use of IL-6 antibodies will also be allowed on study; however, formal enrollment to another investigational study involving IL-6 antibodies is prohibited.

The development of novel treatments and interventions for COVID-19 will be monitored by lead site investigators (Drs. [name] and [name]) as well as other study team members. Appropriate changes to allowed treatments and interventions will be instituted accordingly.

Description of Treatment Regimens

Patients will be randomly assigned to receive a one-time dose of degarelix 240 mg SQ or matching placebo on day 1. The matching placebo will contain equal volume 0.9% saline.

No dose modifications are allowed for degarelix.

Prescribing and Dispensing Study Products

Study medication (Degarelix (Firmagon) 240 mg or placebo) will be dispensed by the local research pharmacist at each site after careful confirmation of treatment assignment.

In addition to best supportive care, each patient will receive a one-time dose of study medications supplied as 2 – 3ml syringes for deep SQ administration on either side of the anterior abdomen in the general perumbilical area.

Treatment 1 - Active Degarelix (2 – prefilled syringes containing 3 ml of reconstituted Degarelix concentrated to 40mg/ml)

Treatment 2 - No active, only placebo (2 – prefilled syringes containing 3 ml of 0.9% saline)

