Viral load kinetics in the two treatment groups over patients' critical period will be monitored from baseline to Day 15. The viral load in plasma will be assessed by the viral RNA measured by a reverse-transcriptase–polymerase chain–reaction (RT-PCR) assay and quantified as \log_{10} copies/ml. Mean change from baseline in SARS-CoV-2 viral RNA load across each sample collection time point will be compared by the treatment groups. The mean value for \log_{10} copies/ml for each week will be calculated and summarized. \log_{10} copies/ml changes from baseline to each week will be summarized. For each week, the sample size, mean, SD, median, minimum, and maximum values for each treatment will be presented. A mixed-effect model of repeated measure (MMRM) for overall changes across all the time point between the two treatment groups using SAS PROC MIXED. A longitudinal graph of \log_{10} copies/ml will be created and presented by 95% confidence intervals of the means.

Serum cytokines TNF- α , IL-1 β , and IL-6, as well as TMPRSS2 expression and anti-viral antibodies will be tested by immunoassays. Mean change from baseline in the cytokine and TMPRSS2 levels, and antibody titers across each sample collection time point will be compared by the treatment groups. The mean value for each week will be calculated and summarized. Mean changes from baseline to each week will be summarized. For each week, the sample size, mean, SD, median, minimum, and maximum values for each treatment will be presented. A mixed-effect model of repeated measure (MMRM) for overall changes across all the time point between the two treatment groups using SAS PROC MIXED. A longitudinal graph of each measurement level will be created and presented by 95% confidence intervals of the means. If a measurement level

is not normally distributed, then a non-parametric method will be used as an alternative analysis approach.

The exploratory analyses will not be adjusted for multiplicity.

AE and SAE analyses

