### 2.4.3 Exploratory Outcome Variables

*Prognostic factors associated with clinical outcomes*

Clinical Factors: Age, use of angiotensin converting enzyme inhibitors, the duration of pre-hospitalization symptoms, or the presence or absence of hypertension, cardiovascular disease, asthma, diabetes mellitus, or COPD

Laboratory Factors D-dimer, IL-6, LDH, ferritin, total WBC, absolute neutrophil count (ANC), absolute lymphocyte count (ALC), or testosterone

*Treatment effect on viral load and cytokines (GLA site only)*

Viral load NP epithelial cells, PBMC

Serum cytokines TNF- $\alpha$ , IL-1 $\beta$ , IL-6

Other TMPRSS2 expression, anti-viral Ab, genomic factors

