described in the primary analysis and each corresponding secondary endpoint analysis (Table 3.7.3.6).

*Viral Load, Cytokines Levels, and TMPRSS2 Expression*

To explore the mechanisms that underlie treatment effect, nasopharyngeal (NP) epithelial or peripheral blood mononuclear cell (PBMC) TMPRSS2 expression, NP and plasma viral load, or serum cytokine (TNF- $\alpha$ , IL-1 $\beta$ , IL-6) levels will be tested among the participants from the Great Los Angeles site only.

Viral load kinetics in the two treatment groups over participants' critical period will be monitored from baseline to day 30. The viral load in plasma will be assessed by the viral RNA measured by a reverse-transcriptase–polymerase chain–reaction (RT-PCR) assay and quantified as  $\log_{10}$  copies/ml. Mean change from baseline in SARS-CoV-2 viral RNA load across each sample collection time point will be compared by the treatment groups. The mean value for  $\log_{10}$  copies/ml for each week will be calculated and summarized.  $\log_{10}$  copies/ml changes from baseline to each week will be summarized. For each week, the sample size, mean, SD, median, minimum, and maximum values for each treatment will be presented. A mixed-effect model of repeated measure (MMRM) for overall changes across all the time point between the two treatment groups using SAS PROC MIXED (Table 3.7.3.7). A longitudinal graph of  $\log_{10}$  copies/ml will be created and presented by 95% confidence intervals of the means (Figure 3.7.3.1).

Serum cytokines TNF- $\alpha$ , IL-1 $\beta$ , and IL-6, as well as TMPRSS2 expression and antiviral antibodies will be tested by immunoassays. Mean change from baseline in the cytokine and TMPRSS2 levels, and antibody titers across each sample collection time point will be compared by the treatment groups. The mean value for each week will be calculated and summarized. Mean changes from baseline to each week will be summarized. For each week, the sample size, mean, SD, median, minimum, and maximum values for each treatment will be presented (Table 3.7.3.8). A mixed-effect model of repeated measure (MMRM) for overall changes across all the time point between the two treatment groups using SAS PROC MIXED. A longitudinal graph of each measurement level will be created and presented by 95% confidence intervals of

the means (Table 3.7.3.9). If a measurement level is not normally distributed, then a non-parametric method will be used as an alternative analysis approach.

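### The antibody-onset aim has no analysis of onset and no rule for patients given convalescent plasma, so donor antibody can be read as the patient's own (exploratory, GLA site only)

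*Protocol*

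**What the plan says.** - **Aim.** The last exploratory endpoint in Protocol 2 reads "To determine the temporal onset of anti-viral antibodies". SAP 2.4.3 lists the variable under a heading restricted to GLA: "Other TMPRSS2 expression, anti-viral Ab, genomic factors".
- **Plasma.** Protocol 6, Best Supportive Care, says that "use of convalescent plasma is not uncommon, is available through an expanded access program and will be allowed prior to or during study enrollment". No rate of use is given.
- **Measurement.** Protocol 10 has "anti-viral antibodies will be tested by immunoassays"; SAP 3.7.3 has "antiviral antibodies will be tested by immunoassays". No isotype, positivity cut-off or other assay detail is stated.
- **Analysis.** Under Protocol 10, mean change from baseline in "antibody titers across each sample collection time point will be compared by the treatment groups", with weekly summaries and an MMRM. SAP 3.7.3 is the same. SAP 3.1.2 takes baseline as the last value before study treatment.
- **Sampling.** Table 1 and its footnotes in Protocol 7 give research blood at Days 1, 8 and 15 and one later draw (footnote F names Day 30), with windows of 2 days either side after Day 1. The Day 1 draw may precede the injection by up to 72 hours. Collection stops at discharge, and a missed draw is not a deviation.
- **Nearest general rule.** SAP 3.6 tabulates concomitant medications by arm, tests them, and provides for adjusting efficacy analyses, where needed, for relevant drugs whose use differs significantly.

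**The concern.** There are two gaps, and they compound each other. First, the aim is a time, but the only planned summaries are mean titres and changes in titre. No rule says when a patient counts as having developed antibody. Second, a patient who receives plasma receives donor antibody. Nothing in the plan excludes, censors, separates or adjusts for that patient's later samples, and no assay feature that would tell donor from own antibody is named. With at most four scheduled draws, one donor-positive sample can settle a patient's apparent onset. What is at stake is whether the reported antibody timing describes the immune response or the timing of transfusions.

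**Working it through.** The plan gives no figure for this point, so there is none to reproduce. The check compares the aim with the analysis, then illustrates size on stated assumptions.

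**1. Aim against analysis.** The aim is the time at which antibody appears. The analysis is mean titre change by visit and an MMRM contrast between arms. Neither yields a time, and without a cut-off none can be derived from them.

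**2. Effect on titre change.** Write own titre as a0 at baseline and a1 at a visit, and donor contribution as d0 and d1, added to it. Then

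observed change = (a1 + d1) − (a0 + d0) = own change + (d1 − d0).

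- Plasma after baseline: d0 = 0, so the change is overstated by d1.
- Plasma before baseline: d0 > 0, so the change is understated by d0 − d1 whenever donor antibody has fallen by the visit.

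The documents give no d0, d1 or usage rate, so neither sign nor size can be fixed.

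**3. Illustration on the share positive.** This is not the planned measure; it shows what would happen to a simple reading of onset. Let s be the share with own antibody at a visit and f the share given plasma. Assume the two are independent and every recipient reads positive. Then

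apparent share = 1 − (1 − s)(1 − f).

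| Own (s) | f = 10% | f = 30% | f = 50% |
|---|---|---|---|
| 30% | 37% | 51% | 65% |
| 50% | 55% | 65% | 75% |
| 70% | 73% | 79% | 85% |

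Positives due to donor antibody alone, (apparent − s)/apparent, run from 4% (s = 70%, f = 10%) to 54% (s = 30%, f = 50%).

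With equal use of 20% in both arms there is no difference between arms, but the share positive is overstated by 0.20 × (1 − s): 14, 10 and 6 points at s = 30%, 50% and 70%. With assumed use of 15% on degarelix and 30% on placebo, the false arm difference is 0.15 × (1 − s): 10.5, 7.5 and 4.5 points.

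**4. Would SAP 3.6 catch it?** With equal use, its test fires only by chance. With assumed use of 40% on placebo and 20% on degarelix, power to flag the difference at the 5% level is about 84% in the full trial (66 and 132 patients). If the test were confined to GLA, power would be about 34% with 17 placebo patients and 21% with 9. Those counts assume GLA enrols either a quarter of 198 (49.5) or its share of the case counts in Protocol 5, 22/(83 + 22 + 51 + 9) × 198 = 26.4, split 2:1.

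**5. Precision.** At about 17 degarelix and 9 placebo patients, the standard error of 57.5% against 65.0% is √(0.575 × 0.425/17 + 0.65 × 0.35/9) = 0.199, or about 20 points. The illustrative 7.5-point difference is under 0.4 standard errors.

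**The case against.** The strongest reply is about weight. The aim is exploratory, confined to one site, sampled on a best-effort basis, unadjusted for multiplicity, and meant to generate hypotheses (SAP 3.7). No efficacy, safety or stopping decision rests on it. All of that stands.

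It can also be said that SAP 3.6 already covers plasma, since the exploratory analyses sit within the efficacy section. In part it does: it could act on a marked imbalance. It names neither plasma nor antibody, depends on a significant test, and does nothing when use is balanced, although onset is then still mis-dated.

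The list of prohibited concurrent treatments in Protocol 6 restricts other investigational COVID-19 drugs before Day 1, which might be read as keeping out earlier plasma. That text and the Best Supportive Care text should be reconciled. The restriction concerns the period before Day 1, so plasma given afterwards is allowed on either reading.

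Three stronger readings are tempting, and the documents do not support them:

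- **That an immunoassay cannot tell donor from own antibody.** The assay is unspecified. What can be said is that no separation is planned.
- **That placebo patients would falsely appear to make antibody earlier, because sicker patients get plasma.** The documents do not say who gets plasma or how often. The arm-specific shares above are assumptions.
- **That plasma before Day 1 makes change from baseline meaningless or biases the arm comparison.** It can blunt the change, but plasma given before randomisation is balanced between arms in expectation. Only later use can differ systematically by arm.

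**Conclusion.** The point holds for this one exploratory, GLA-only aim. As written, the analysis does not estimate onset and mixes plasma recipients with everyone else, so donor antibody can be counted as the patient's own even when plasma use is equal in the two arms. The conclusion rests on the absence of any rule in either document and on plasma carrying antibody that the chosen assay detects. The effect on the planned titre change is unknown in size and direction; the percentages in the working show only that it need not be trivial. A reader might infer that the trial's efficacy findings are at risk. They are not: the primary, secondary and safety analyses do not use antibody data.

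**What to change.** In SAP 3.7.3 and Protocol 10:

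1. State a positivity cut-off, and define onset as the interval between the last negative and first positive sample. Analyse it as interval-censored, with days since symptom onset as the time axis. SAP 3.5.2 already lists the days of symptoms before hospitalisation.
2. Censor antibody samples at the first plasma infusion, and set aside patients given plasma before the Day 1 draw. Tie the rule to the draw, because that sample may precede the injection by up to 72 hours.
3. Require the infusion date in the concomitant-medication log (Form 6, SAP Appendix 5.3.2). The documents do not say that the log captures it.
4. Report plasma recipients separately by arm.
5. Add a sensitivity analysis on all samples. Plasma given after randomisation may be related to clinical course and could differ by arm, so censoring there may be informative and could replace contamination with selection.

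The cost is SAP text and a minor protocol wording change, which needs IRB review (Protocol 12), together with fewer usable samples. With few draws at a single site, the onset estimate will be imprecise, and the report should say so.
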